3.2 Primary Study Endpoints

Primary Efficacy End Point: The primary end points after 8 weeks of treatment include the following: (1) the change in the Ocular Surface Disease Index (OSDI) which is a patient subjective rating scale; the Clinical Global Impression (CGI) of change in dry eye disease symptoms (physician's rating) and Subject Global Assessment (SGA) of overall change from baseline (patient's rating) will serve as anchors to OSDI, as has been described previously²⁹; (2) a mean reduction in ocular surface staining as measured by Rose Bengal dye staining and (3) the change in ocular surface redness score OR slit-lamp examination.

Primary Tolerability End Point: The change in the test substance tolerance between Day 1 (post-dose) and at weeks 2, 4, 6 and 8.

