3.2.6 Tolerability End Point: Test Substance Tolerance (Visual Analogue Scale)

Subjects will assess their tolerance to the administration of the test medication (placebo/ study drug), utilizing a Visual Analog Scale (VAS). The VAS is a 100 mm horizontal line with verbal descriptors at either end. The VAS ratings will be completed after administration of the test medication on Day 1 (post-dose), week 2, week 4, week 6 and week 8. Subjects will place a single slash mark across the horizontal line between the end labeled “completely intolerable” (0 mm) and “easily tolerable” (100mm). The VAS rating is as follows:

Please rate the degree of comfort or lack of comfort associated with administering the eye drop by making one slash mark on the line below:

Visual Analogue Scale

On the scale of 0 to 100 seen below, please mark where you would rate your tolerability to administration of the test drug.

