4.4.2 Data Collection and Follow-up for Withdrawn Subjects

If a subject withdraws from the study prior to 8 weeks, the subject will be asked to complete the procedures outlined in the 10 week visit as well as the Test Substance Tolerance scale from 8 weeks, as soon as possible. Subjects who voluntarily withdraw from the study between 8 weeks and 10 weeks will be asked to complete procedures outlined in the 10 weeks visit as soon as possible. Subjects who are withdrawn due to adverse events will be followed at least until resolution or stabilization of the adverse event.

If the subject remains in the study for safety evaluation, follow-up visits will be scheduled according to the schedule of visits and procedures found in the synopsis.

5 Study Drug

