The subjects will be monitored frequently (at 2 weekly intervals) to ensure that they are not subjected to any undue risks during the wash out period or during the course of the study. Additionally, they will be warned of the possible signs and symptoms of clinical worsening of DED, and advised to contact the research team immediately in case any of those symptoms occur. Subjects will also be encouraged to contact the research team in case they experience any ocular discomfort during the wash out period or during the course of the study. The subject's condition will be monitored by the physician (Principal Investigator) at each study visit, as well as at any interim visit (in case of adverse symptoms, as mentioned above). Any worsening of DED or any adverse event due to the study drug will be recorded. In case of clinical worsening, based on the individual subject's clinical condition, one or more of the following therapeutic decisions may be implemented: (1) Increasing the frequency of use of artificial tears, (2) Re-starting the use of anti-inflammatory therapy (Restasis/ corticosteroids), (3) Withdrawal of the use of study drug (if worsening occurs during the course of the study). The decision will be made by the physician (Principal Investigator) based his clinical judgment as per the individual subject's clinical condition. If additional anti-inflammatory therapy (Restasis/ corticosteroids) is instituted during the wash-out period, the subject will be excluded from the study. Also, if additional anti-inflammatory therapy (Restasis/ corticosteroids) is instituted during the course of the study and/or the study drug is

withdrawn, the subject will be excluded from the study. After any clinical worsening is noted, the subjects will be followed more closely (weekly) until complete resolution of symptoms and return to the subject's previous baseline.

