5.7 Rescue Plan

The research staff, including the PI, will be masked to randomization, thus will not be aware if a particular subject receives study drug or placebo. Subjects will be monitored by the Principal Investigator at each study visit. Any worsening of DED or any adverse event (AEs) will be recorded and in the case of AEs followed to resolution. In case of clinical worsening/ adverse event(s), based on the individual subject's clinical condition, one or more of the following therapeutic decisions may be implemented:

- (1) Increasing the frequency of artificial tears use,
- (2) Re-starting the use of anti-inflammatory therapy (Restasis/ corticosteroids),
- (3) Discontinue the study drug.

The decision will be made by the Principal Investigator based on his clinical judgment and the individual subject's clinical condition. If additional anti-inflammatory therapy (Restasis/ corticosteroids) is instituted and/or the study drug is discontinued, the subject will be withdrawn from the study. If an adverse event is severe enough to discontinue the subject from the study, the PI may decide to break the subject's randomization code if it seems relevant to the treatment of his/her ocular condition at that time. He/ She will receive the treatment required for his/ her eye condition as per established clinical guidelines.

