6.5.3 Visit 3: *Week 2 (± 2 days)*

Treatment Visit (after any dose for that day)

- Vital Signs
- Ophthalmic Examination (slit lamp examination, Ocular surface redness score)
- Physical Inspection of the Nose and Oropharynx
- OSDI
- Visual Analogue Scale
- Clinical Global Impression, Subject Global Assessment
- Review the subject's diary and record changes in concomitant medication, deviations from drug schedule and adverse events.
- Subjects will be given study medication, sufficient to last for 2 weeks, to take home.

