7.1 Sample Size Determination

Our intention is to have at least 30 subjects in each group (study drug/ vehicle) complete the study. This number is based on published reports of similar randomized clinical trials designed to determine

efficacy and tolerability of a test drug in Dry Eye Disease.³²⁻³⁴ A total of 72 subjects will be enrolled so that even if 20% of subjects are unable to complete the study, we will still remain with the intended number of subjects who complete the study (at least 30 subjects in each group). Subjects will be randomized to either of the two groups (#1, placebo; #2, study drug) as explained in section 5.3. However, all subjects who received at least two weeks of treatment with study eye drops and attended at least the first post-treatment (week 2) follow up visit will be included for analysis.

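### The primary tolerability VAS excludes subjects who stop before Week 2 and has no scoring rule for those who stop later, so it can overstate how well the drops are tolerated

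*Combined protocol and SAP*

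**What the plan says.** All references are to the combined protocol and SAP.

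- **Endpoint.** Section 3.2 names as the primary tolerability endpoint "The change in the test substance tolerance between Day 1 (post-dose) and at weeks 2, 4, 6 and 8". It serves the primary tolerability objective in Section 2, which is whether patients can tolerate eight weeks of the drops.
- **When it is rated.** Section 3.2.6 states: "The VAS ratings will be completed after administration of the test medication". The scale runs from 0 mm (intolerable) to 100 mm (easily tolerable).
- **What stopping leads to.** Section 5.7 says that if "the study drug is discontinued, the subject will be withdrawn from the study". Section 5.6 says that if the drug is "withdrawn, the subject will be excluded from the study". Neither says what happens to the subject's tolerability data.
- **Exit rating.** Section 4.4.2 asks a subject who leaves before Week 8 for the Week 10 procedures "as well as the Test Substance Tolerance scale from 8 weeks, as soon as possible". It requires no preceding dose and does not say which visit the rating represents.
- **Analysis set.** Sections 7.1 and 7.3 keep only subjects with at least two weeks of treatment who attended the Week 2 visit.
- **Method.** Section 7.2 plans descriptive statistics for the primary endpoints, a signed-rank test for OSDI and a chi-square test for qualitative variables. It names no test for the VAS and no handling of missing or post-stopping values.
- **Expected loss.** Section 7.1 sizes the trial so that it holds up "even if 20% of subjects are unable to complete the study".

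**The concern.** On a tolerability scale the missing values are not a random sample. A subject who finds the drops hard to bear is more likely to stop, and so more likely to have no on-treatment rating at Weeks 4, 6 and 8. If the by-visit summary uses only those still on the drops, it describes people who tolerated them. It could show similar comfort in both arms when one arm was less comfortable.

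Because the rule is open, three analyses would be defensible once data are in: observed ratings only, exit rating placed at Week 8, or exit rating carried to every remaining visit. They can give different answers on a primary endpoint, and the choice could be made with the data in view.

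**Working it through.** **Step 1. Follow a subject through the plan.**

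| When the subject stops | VAS ratings asked for | Treatment under Section 7 |
|---|---|---|
| Before two weeks, or no Week 2 visit | Day 1, exit rating | Subject removed, so any exit rating goes unused |
| After Week 2, before Week 8 | Day 1, Week 2, later ratings while on drops, exit rating | Subject kept; no rule for the exit rating or the remaining visits |
| Completes | Day 1, Weeks 2, 4, 6, 8 | Used |

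The exclusion in the first row is explicit. The gap in the second row comes from silence.

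**Step 2. How many subjects.** The plan gives no expected VAS mean, SD or difference, so there is no VAS figure to reproduce. Its enrolment of 72 is reproduced by 60 × 1.2 = 72. Allowing properly for 20% loss gives 60 / 0.8 = 75, and 72 × 0.8 = 57.6 completers. That shortfall is a separate matter; only the 20% is used here. 0.20 × 72 = 14.4, taken as 14 stoppers. 0.20 × 36 = 7.2, taken as 7 per arm. An even 36 per arm is an assumption.

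**Step 3. Difference hidden by an observed-only analysis.** Assumptions: completers have mean change 0 in both arms, and stoppers truly fall by F mm from their Day 1 rating. With k drug-arm and m placebo stoppers, the observed-only difference is 0. Counting everyone, drug minus placebo is

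D = −F × (k − m) / 36.

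| Stoppers, drug v placebo | F = 20 | F = 40 | F = 80 |
|---|---|---|---|
| 7 v 7 | 0 | 0 | 0 |
| 10 v 4 | −3.3 | −6.7 | −13.3 |
| 12 v 2 | −5.6 | −11.1 | −22.2 |

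For example, −80 × 10 / 36 = −22.2 mm. In the 7 v 7 case each arm's own mean is still overstated by F × 7 / 36, that is 3.9, 7.8 or 15.6 mm.

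**Step 4. Dependence on Day 1.** The endpoint is a change. A subject who rates 25 mm after the first dose and 25 mm at exit has F = 0. If all stoppers are like this, D = 0 in every row. Scoring them by carrying the exit value forward would record them as unchanged.

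**Step 5. The completion endpoint.** Section 3.4 counts the proportion completing eight weeks of treatment. With 7 of 36 stopping in an arm, completion among all randomised is 29 / 36 = 80.6%. If Section 7.3 sets the denominator and 3 of the 7 stopped before Week 2, it becomes 29 / 33 = 87.9%. If all 7 stopped before Week 2, it becomes 29 / 29 = 100%.

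**The case against.** Three stronger readings are tempting, and the documents do not support them.

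- **A reader might infer that the plan drops the least tolerant subjects from the result.** After Week 2 it does not. They stay in the analysis set with their earlier ratings, and an exit rating is requested. Section 4.4.2 calls it the Week 8 scale, which can be read as the Week 8 assessment brought forward. Its use is unspecified, not ruled out. Only the removal before Week 2 is explicit.
- **A reader might infer that the exit rating contradicts Section 3.2.6.** That section sets no interval between dose and rating, and a rating made as soon as possible could follow closely on the last drop. This is a tension, not a certain breach.
- **A reader might infer a definite bias against the drug arm.** Suppose stayers and all vehicle subjects rate 85, and 10%, 15% or 20% of the drug arm rate 25 and stop. The raw Week 8 gap is then share × 60 = 6, 9 or 12 mm. This uses raw scores, puts all stopping in one arm, and on the change scale requires stoppers to have rated 85 on Day 1. From a Day 1 rating of 55 the gap is share × 30 = 3, 4.5 or 6 mm; from 25 it is 0. Section 1.5 notes that placebo subjects risk worsening disease, and Sections 5.6 and 5.7 make worsening a route off treatment, so vehicle-arm stopping is foreseeable.

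It is also fair to say that stopping is counted by the completion endpoint and that adverse events are evaluated in all exposed subjects (Section 8.6). That limits the harm but does not repair the VAS. Completion is itself weakened if Section 7.3 sets its denominator, and Section 8.1 allows adverse-event withdrawals to be replaced.

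Finally, Section 7.2 plans description for primary endpoints, so a rank test is an addition. Even a descriptive table needs a rule for who is in it.

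**Conclusion.** The point holds as a gap in a primary endpoint. Subjects who stop before Week 2 are excluded by rule, and later stoppers have an exit rating with no assigned visit, no link to a dose and no stated use. The by-visit VAS can therefore overstate tolerability.

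The size cannot be settled from the documents. The range of 0 to about 22 mm rests on 36 per arm, 14 stoppers in all, no mean change in completers, and assumed falls of 20 to 80 mm. The upper end needs both a 12 v 2 split and an 80 mm fall. Equal stopping, or low ratings already on Day 1, brings the between-arm figure to about 0.

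**What to change.** 1. **Sections 7.1 and 7.3.** Analyse tolerability and completion in all subjects who received at least one dose, by randomised arm, including any who were later replaced.
2. **Section 4.4.2.** Have the exit VAS rate the last dose taken, record the date of that dose, and state that the rating counts for the remaining scheduled visits through Week 8.
3. **Section 7.2.** Give any subject who stops because of intolerance the worst rank at later visits, whether or not an exit VAS exists. Carry-forward alone is not enough, because on a change score it can record an intolerant subject as unchanged. Compare arms by a rank test and show the observed-only change as a sensitivity analysis.
4. **Sections 5.6 and 5.7.** Reconcile excluded with withdrawn, so that neither word can be taken to remove a subject's data from analysis.

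The cost is a few sentences and one date field; the exit rating is already requested. The ranking depends on the recorded reason for stopping, which should be settled without knowledge of the arm. It also assumes that tolerance would not have improved with continued use.

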3.2.1 Efficacy End Point: Ocular Surface Disease Index (OSDI)

The OSDI rating scale has twelve questions in three discrete areas, with responses rated on a five point scale. Subjects will complete this scale on Day 1 prior to first dose (Baseline), week 2, week 4, week 6, week 8 and week 10. The questions and scoring system are shown below:

HAVE YOU EXPERIENCED ANY OF THE FOLLOWING DURING THE LAST WEEK:

	All of the time	Most of the time	Half of the time	Some of the time	None of the time
1. Eyes that are sensitive to light?	4	3	2	1	0
2. Eyes that feel gritty?	4	3	2	1	0
3. Painful or sore eyes?	4	3	2	1	0
4. Blurred Vision?	4	3	2	1	0
5. Poor vision?	4	3	2	1	0

HAVE PROBLEMS WITH YOUR EYES LIMITED YOU IN PERFORMING ANY OF THE FOLLOWING DURING THE LAST WEEK:

	All of the time	Most of the time	Half of the time	Some of the time	None of the time	
6. Reading?	4	3	2	1	0	N/A
7. Driving at night?	4	3	2	1	0	N/A
8. Working with a computer Or bank machine (ATM)?	4	3	2	1	0	N/A
9. Watching TV?	4	3	2	1	0	N/A

HAVE YOUR EYES FELT UNCOMFORTABLE IN ANY OF THE FOLLOWING SITUATIONS DURING THE LAST WEEK:

	All of the time	Most of the time	Half of the time	Some of the time	None of the time	
10. Windy conditions?	4	3	2	1	0	N/A
11. Places or areas with Low humidity (very dry)?	4	3	2	1	0	N/A
12. Areas that are air conditioned?	4	3	2	1	0	N/A

3.2.2 Efficacy End Point: Clinical Global Impression (CGI)

At each visit, the physician (Principal Investigator) will use his clinical evaluation (all signs and symptoms taken together) to provide a global assessment of the patients' change in Dry Eye symptoms and signs. The CGI is as follows:

Question (to physician): In general, compared with the patients' dry eye symptoms and signs at baseline, how would you characterize his/ her overall signs and symptoms now?

The responses will be categorized on a seven point scale as follows:

- Marked worsening
- Moderate worsening
- Minimal worsening
- Unchanged
- Minimal improvement
- Moderate improvement
- Marked improvement

3.2.3 Efficacy End Point: Subject Global Assessment (SGA)

At each visit, the subjects will be asked to assess their overall change from baseline. The SGA is as follows:

Question 1 (to subject): Compared with your first visit, how are your dry eye symptoms now?

The responses will be categorized on a five point scale as follows:

- Much worse
- Worse
- About the same
- Improved
- Much improved

Question 2 (to subject): Compared with your first visit, how is the mucous strings or mucous discharge from your eyes now?

[figure not shown]
The responses will be categorized on a five point scale as follows:

- Much worse
- Worse
- About the same
- Improved
- Much improved

3.2.4 Efficacy End Point: Ocular surface Rose Bengal dye staining score

Ocular surface staining will be assessed using Rose Bengal dye. Saline moistened 1% Rose Bengal dye impregnated strips will be used to instill the dye on the inferior palpebral conjunctiva and scoring of corneal and conjunctival staining will be performed by a slit lamp examination after 15 seconds using the grading system described by the 1995 NEI workshop.³⁰ Corneal staining will be graded in 5 zones

and conjunctival staining will be graded in 6 zones. Each zone will be graded from 0 to 3 based on the density of punctate staining. The final staining score will be the sum of individual scores from all 11 zones (5 corneal, 6 conjunctival). The scoring pattern is represented below.

[figure not shown]
Complete ocular surface staining clearance means absence of any punctate or confluent staining with Rose Bengal dye defined as Rose Bengal staining score of 0.

3.2.5 Efficacy End Point: Ocular surface redness score

Ocular surface redness (nasal or temporal) will be assessed using the Validated Bulbar Redness grading scale (VBR).³¹ The VBR consists of a set of ten images illustrating different degrees of ocular surface redness (OR), ranging from normal to severe, and each image is assigned a value in an order of ascending severity. Colored copies of these images will be made using a single printer and constant settings and put up in all the examination rooms. Subjects will be examined by a slit-lamp at 10X magnification using direct diffuse illumination (slit fully opened, angled at 30°- 50° approximately; at half illumination intensity with rheostat set to maximum voltage) and the bulbar conjunctival injection of the subject's eye (nasal and temporal) will be compared to the reference images and graded accordingly. To maintain uniformity, all subjects will be graded by a single physician (Principal Investigator) under constant illumination conditions. The subjects will be asked to look at nasal or temporal fixation marks while the physician will examine the temporal or nasal bulbar conjunctivae, respectively.

Photographic anchors and their respective grades for ocular surface redness are shown below:

□

[figure not shown]
3.2.6 Tolerability End Point: Test Substance Tolerance (Visual Analogue Scale)

Subjects will assess their tolerance to the administration of the test medication (placebo/ study drug), utilizing a Visual Analog Scale (VAS). The VAS is a 100 mm horizontal line with verbal descriptors at either end. The VAS ratings will be completed after administration of the test medication on Day 1 (post-dose), week 2, week 4, week 6 and week 8. Subjects will place a single slash mark across the horizontal line between the end labeled “completely intolerable” (0 mm) and “easily tolerable” (100mm). The VAS rating is as follows:

Please rate the degree of comfort or lack of comfort associated with administering the eye drop by making one slash mark on the line below:

Visual Analogue Scale

On the scale of 0 to 100 seen below, please mark where you would rate your tolerability to administration of the test drug.

3.3 Secondary Endpoints

The secondary study endpoints will include:

1. Change in tear secretion as measured by Schirmer I test
2. The proportion of eyes achieving complete ocular surface staining clearance after treatment
3. Visual acuity change
4. Change in frequency of administration of artificial tears or concomitant eye drops
5. Change in number of corneal filaments (slit-lamp examination)

Corneal filaments are mucous tags that are adherent to the surface of cornea. The number of such mucus tags will be counted on each clinical examination (slit-lamp examination).

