5.1 Description

The study drug, rhDNase1, will be supplied as a 1 mg/ml (0.1%) solution for administration as topical eye drops. The control group will receive drug vehicle eye drops as placebo.

Each subject will receive either 0.1% rhDNase1 (study drug) or drug vehicle (placebo) solution, as a single eye drop in each eye four times a day (QID) for eight weeks. Except for the first dose on Day1, subjects will self-administer the test medication eye drops at home.

Subjects will not be charged for the test medication in any way (neither the cost of the medication nor its dispensing cost).

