5.3 Method for Assigning Subjects to Treatment Groups

This Randomized placebo-controlled trial will have two study groups. Subjects will be randomly assigned to one of two groups (#1, #2). Group #1 will receive placebo (drug vehicle; control group) and Group #2 will receive study drug (rhDNase 0.1%; test group). We will use a computer-based random code generator (Research Randomizer; <http://randomizer.org/>) to generate 1 set of 72 non-unique, unsorted numbers with a range from 1 to 2 representing the group number (#1 is control group, #2 is test group). Each subject will be assigned a study identification (ID) number at screening, eg. subject #1, subject #2, subject #3 and so on. Based on the randomizer generated table, subject #1 will receive either placebo (#1 group) or study drug (#2 group). This will be repeated for each subject. For reproducibility purpose, we will document the final randomization schedule and the random SEED number used to generate the schedule. Randomization will be performed by the Illinois Eye and Ear Infirmary's pharmacy, and neither participants nor research staff will be aware of the assigned treatments. The person conducting the randomization will remain masked as well.

The study identification (ID) number will be used on all study-related documents. To maintain confidentiality, the subject's name will not be recorded on any study document other than the informed consent form. The drug vial number will be linked to the patient identification number.

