6.5 Study Assessments

The following detailed procedures are performed at the designated clinic visit. All results will be documented on the subject's medical/research charts, source documents, and CRFs as required. All ophthalmic procedures will be performed on both eyes.

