7.2 Statistical Methods

Descriptive statistics will be used for all primary and secondary endpoints, when appropriate.

We will define outcome measures on the basis of the change for each subject from baseline to each follow-up point, controlling for chance imbalances in the mean baseline values between treatment groups. A Wilcoxon Signed-rank test will be used for paired comparison of quantitative variables (OSDI score) between the baseline and each post-baseline time points. Chi-square test will be used to compare qualitative variables (Investigator's rating scale/ changes in concomitant medications) between the 2 groups. Two-sided $P < .05$ will be considered statistically significant for all comparisons. 95% Confidence interval will be provided for comparison between the investigational drug and placebo for the primary efficacy, the primary safety, and the secondary endpoints.

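### Staining clearance is counted by eye while subjects are randomised, and Section 7.2 makes no allowance for two eyes from one subject, so by default its confidence interval is too narrow.

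*Combined protocol and SAP*

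**What the plan says.** Section 3.3 makes the eye the unit of this endpoint: "The proportion of eyes achieving complete ocular surface staining clearance after treatment". Section 3.2.4 makes clearance binary, "defined as Rose Bengal staining score of 0".

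Treatment is allocated by subject (Section 5.3), and Section 5.1 gives the allocated product "as a single eye drop in each eye four times a day (QID) for eight weeks". Section 6.5 adds: "All ophthalmic procedures will be performed on both eyes". Rose Bengal staining is done at screening and again at Week 8 (Sections 6.5.1 and 6.5.6).

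On analysis, Section 7.2 says that a "Chi-square test will be used to compare qualitative variables" between the two groups, sets a two-sided 5% level for all comparisons, and promises: "95% Confidence interval will be provided for comparison between the investigational drug and placebo for the primary efficacy, the primary safety, and the secondary endpoints". The documents contain no study-eye rule, no worse-eye or both-eyes rule, no averaging over eyes and no method for correlated eyes. Section 7.3 defines the analysis population by subject and does not say which eyes count.

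**The concern.** Two eyes of one person, given the same drops for the same eight weeks, tend to clear or fail to clear together. Because both eyes are always in the same arm, that correlation adds to the variance of the difference between arms; nothing within the subject cancels it. A chi-square test or a standard interval for two proportions treats every eye as a separate observation. It credits an arm of 30 subjects with up to 60 independent results.

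At stake is the precision claimed for the clearance result. A chance difference between arms would be declared significant more often than the stated 5%, and the interval would cover the true difference less often than 95%.

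**Working it through.** **Inputs from the documents.** At least 30 completers per arm (Section 7.1); two eyes treated and examined per subject (Sections 5.1 and 6.5); two-sided 5% level and 95% interval (Section 7.2). The plan states no clearance rate, correlation between eyes, power or interval width for this endpoint, so there is no figure of its own to reproduce.

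**Assumptions.** Correlation between eyes, rho, of 0.3, 0.5 or 0.8. Every subject contributes two eyes, hence 60 eyes per arm. For interval widths, 20% clearance in both arms.

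**Formulae.** With two eyes per subject on the same treatment:

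- design effect = 1 + (2 − 1) × rho = 1 + rho
- correct SE / eye-level SE = sqrt(1 + rho)
- effective independent eyes per arm = 60 / (1 + rho)
- actual type I error = 2 × [1 − Phi(1.96 / sqrt(1 + rho))]
- eye-level half-width = 1.96 × sqrt(2 × 0.20 × 0.80 / 60) = 14.3 points; correct half-width = 14.3 × sqrt(1 + rho)

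| rho | SE factor | Effective eyes per arm | Type I error | Coverage of the eye-level 95% interval | Correct half-width |
|---|---|---|---|---|---|
| 0 | 1.00 | 60 | 5.0% | 95.0% | ±14.3 |
| 0.3 | 1.14 | 46 | 8.6% | 91.4% | ±16.3 |
| 0.5 | 1.22 | 40 | 11.0% | 89.1% | ±17.5 |
| 0.8 | 1.34 | 33 | 14.4% | 85.6% | ±19.2 |

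The SE factor and the error rate do not depend on the number of subjects.

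**Simulation.** An eye-level chi-square test was simulated with 40,000 replicates, 30 or 36 subjects per arm and clearance of 10%, 20% or 30%. The error rate was 8.4–8.9% at rho 0.3, 11.1–11.5% at 0.5 and 14.7–15.4% at 0.8, against 4.9–5.4% at rho 0. This agrees with the formula and is slightly higher at the largest correlation.

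**If some subjects contribute one eye.** Inclusion criterion 5 (Section 4.1) asks for staining of at least 1 without saying in which eye, so some eyes may have nothing to clear. With m eyes per subject, the design effect is 1 + rho × sum of m(m − 1) / sum of m. As an illustration, let 15 of the 30 subjects contribute two eyes and 15 contribute one. The sums are 30 and 45, so the design effect is 1 + 0.67 × rho. At rho 0.5 it is 1.33, the SE factor is 1.15 instead of 1.22, and the type I error is about 9% instead of 11%.

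**A per-subject definition.** Suppose clearance means both eyes clear, with 10% clearance per eye, rho 0.3 and both eyes stained (all assumed). Then P(both clear) = 0.10² + 0.3 × 0.10 × 0.90 = 0.037. The half-width is 1.96 × sqrt(2 × 0.037 × 0.963 / 30) = 9.6 points. The uncorrected eye-level half-width is 1.96 × sqrt(2 × 0.10 × 0.90 / 60) = 10.7 points. The per-subject interval is narrower here because it estimates a different, rarer event.

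**The case against.** The strongest reply is that the faulted analysis is never written down. Section 7.2 illustrates its chi-square test with the physician's rating and changes in concomitant medication, both subject-level, and does not mention clearance. The same section frames outcomes as each subject's change from baseline, and Sections 7.1 and 7.3 count subjects. The endpoint is one of five secondary ones in a Phase I/II trial of tolerability and preliminary efficacy, where descriptive statistics are planned when appropriate. Clustering does not bias the difference in proportions, and no sample size or stopping rule rests on this endpoint.

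Part of this stands. A reader might infer that the plan prescribes an eye-level chi-square test for clearance; it does not. That analysis is the default reading, because no other between-group test for qualitative data is given. A reader might also infer that each arm supplies 60 eyes to the endpoint. Section 6.5 has both eyes examined, but no text says both are counted, and eligibility does not require staining in each.

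The rest does not remove the problem. Framing outcomes by subject does not turn a proportion of eyes into a proportion of subjects, and Section 3.4 does use subjects for its own proportion. The interval is promised for the secondary endpoints without exception, so a method for this one is needed.

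**Conclusion.** The point holds as a default-reading problem. An analyst who follows Section 7.2 for the endpoint in Section 3.3 would obtain an interval that is too narrow and a test that rejects too often. The direction is the same for any positive correlation between eyes; the size depends on a correlation the documents do not give.

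The factors of 1.14 to 1.34 and error rates of about 9% to 14% are the case in which every subject contributes two eyes, at assumed correlations of 0.3 to 0.8. They fall towards 1 and 5% as more subjects contribute a single eye. The weakness concerns the precision of one secondary endpoint. It does not touch its point estimate or the trial's sample size, and the documents do not support saying that a wrong p-value is already planned.

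**What to change.** Keep the eye as the unit in Section 3.3 and limit the denominator to eyes with a Rose Bengal score of at least 1 at screening, the only staining assessment before treatment. Otherwise an eye that scored 0 at entry could count as cleared. In Section 7.2, state that the difference in clearance proportions at Week 8 and its 95% interval are estimated by GEE, or with a cluster-robust variance, with the subject as cluster.

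The cost is one sentence in Section 7.2, a short qualification of the denominator in Section 3.3, and a wider interval. No new data, visits or enrolment are needed.

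A per-subject definition, such as score 0 at Week 8 in every eye that was stained at screening, is a valid alternative. It removes the clustering, but it changes the endpoint in Section 3.3 and what is estimated, and its interval is not necessarily wider. Either choice should be fixed before unblinding, so that eye-level and subject-level results are not chosen between afterwards.
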